### ***Concomitant medications***

The use of all non-study drugs (including over-the-counter medications) from 14 days before starting study therapy through the end of experimental treatment will be monitored and recorded. In addition, if a grade 3 or higher AE or SAE occurs within 28 or fewer days after completion of experimental phase therapy, then the use of all non-study drugs (including over-the-counter medications) during the interval from study drug completion to AE/SAE onset will be recorded. The use of all non-study drugs (including over-the-counter medications) will be recorded at this study visit.

Concomitant antimicrobials with known antituberculous activity (amoxicillin/clavulanic acid, amikacin, kanamycin, streptomycin, moxifloxacin, ofloxacin, ciprofloxacin, levofloxacin, sparfloxacin, gatifloxacin, gemifloxacin, linezolid, capreomycin, cycloserine, ethionamide, para-aminosalicylate sodium) should not be used during the study phase therapy. A second statin should not be used during study phase therapy. Any patient who receives more than 2 doses of any of the medications listed above will be classified as being on a non-study regimen. Antimicrobials with no known antituberculous activity may be prescribed for intercurrent infections at the discretion of the investigator.

Ethanol can exacerbate the potential hepatotoxicity of isoniazid, rifampin, and pyrazinamide. Participants will be counseled to abstain from alcohol while on TB therapy.

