***Targeted symptom assessment***

Participants will be asked whether they have experienced any of the following since the last study visit: fevers, sweats, cough, rash, itching, jaundice, nausea, vomiting, diarrhea, loss of appetite, vision problems, numbness/tingling of extremities, headache, joint pain, eye pain. In addition, patients will be asked whether they have had other symptoms (not listed above); if yes, then these symptoms will be recorded and graded. In addition, targeted diagnostic evaluations may be indicated to determine the underlying cause of symptoms and their association with study drug use.

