### ***Exclusion criteria:***

- a) A history of severe adverse reactions to any statin or any other study agent or contraindications to use of statins.
- b) Current use of statins or other lipid-lower agents;
- c) Clinical indication for statin therapy based on cardiovascular risk:
  - 1) Familial hypercholesterolemia
  - 2) Previous history of myocardial infarction or stroke
- d) For HIV-positive individuals, a CD4+ T-cell count <350/mm^3
- e) Use of antiretroviral drugs
- f) Hemoglobin concentration less than 8 g/dL;
- g) Baseline creatinine kinase elevation more than three times the upper limit of normal
- h) Abnormal baseline laboratory values
  - 1) Baseline alanine aminotransferase (ALT) concentration more than 2.5 times the upper limit of normal (Grade 1)
  - 2) Serum creatinine concentration more than twice the upper limit of normal;
  - 3) Serum total bilirubin level greater than twice the upper limit of normal
  - 4) Platelet count < 100,000/mm^3
  - 5) ANC <1,000/mm^3
- i) Pregnant or breastfeeding;
- j) Silico-tuberculosis.
- k) Currently receiving TB treatment
- l) Serologies or PCR positive for viral hepatitis (Hepatitis, B, C)
- m) Concomitant disorders or conditions for which isoniazid, rifampin, pyrazinamide, or ethambutol is contraindicated. These include cirrhosis, acute liver disease of any cause, acute uncontrolled gouty arthritis and peripheral neuropathy.
- n) Any medical or psychological condition which, in the view of the study investigator, makes study participation inadvisable.
- o) Infection with an isolate determined to be resistant to rifampin by GeneXpert.
- p) More than five days of anti-tuberculosis treatment within the previous 3 months
- q) Planned or current use of cyclosporine, tacrolimus, erythromycin or colchicine
- r) CNS TB
- s) Extra-pulmonary TB only, not in combination with pulmonary TB
- t) History of TB

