### ***HIV-Infected Individuals***

HIV-infected individuals and HIV-uninfected individuals will be included in this study. HIV-infected individuals with CD4 <350 cells/mm^3 will be excluded in this study, as these patients are at increased risk of death and may be better served by individualized (non-study) TB and HIV therapy. If one or both of the proposed experimental regimens is demonstrated to be effective and safe in this study, then subsequent future studies including individuals with advanced AIDS may be warranted. This study will not enroll participants with HIV infection who are taking antiretroviral therapy. For patients with active TB and CD4 cell counts >50/mm^3 who are not already taking ART, initiation of ART is recommended after 2 months of TB treatment. HIV-infected individuals in South Africa are routinely treated with fixed-dose combination pills containing efavirenz, tenofovir, and emtricitabine. Efavirenz is known to lower the mean AUC of pravastatin by ~40%. Therefore, HIV-infected individuals receiving antiretroviral drugs will be excluded from the study. If a participant is already enrolled in the study, and they require antiretroviral therapy, they will be taken off of study medicines and referred to the clinics for treatment with TB and HIV therapy.

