### Drug-drug interactions

Medications that may cause drug interactions with pravastatin include fibrates, erythromycin, niacin, and many others. These drug interactions may result in side effects or complications such as increased levels of medicine in the blood and an increased risk of developing serious muscle problems. The metabolism of pravastatin is not significantly mediated by CYP enzymes. However, pravastatin is a substrate of MRP2 and the uptake transporter OATP2. Recent studies have illustrated differences in the interaction potential of the different statin drugs. Thus, itraconazole increased the AUC of simvastatin acid at least tenfold but had no significant effect on that of pravastatin. Furthermore, combination therapy with the HIV protease inhibitors ritonavir and saquinavir increased the median AUC(0–24) of simvastatin 30-fold, but decreased that of pravastatin by 50%. Pravastatin is a substrate of both influx and efflux transporters, and although significant interactions mediated by induction of pravastatin metabolism are not likely, the *in vivo* effects of induction of transporters are largely unknown.

Rifampin caused a statistically significant decrease in the plasma concentration of pravastatin given as a single oral dose to healthy subjects. However, the effect of rifampin varied greatly between subjects. The mean rifampin-induced decrease in pravastatin concentration was considerably smaller than that observed previously for simvastatin. Unlike simvastatin and its metabolite (simvastatin acid), in which steady-state AUC is reduced by ~90% by rifampin (69), requiring co-administration with rifabutin to obtain adequate drug exposures, pravastatin AUC is reduced by only 30-50% during co-administration with rifampin (70).

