### ***Decision-making algorithm for pravastatin safety/PK study:***

Scenario/Pravastatin Dose	Safe/tolerable?	<math>AUC_{0-24}</math> reduction	Decision
1 40 mg daily	Y	=	Increase dose to prava 80 mg and enroll additional participants
2 40 mg daily	N	=	Enroll 5 additional participants (10 total) and discontinue study

3 80 mg daily	N	=	Discontinue study
4 80 mg daily	Y	< 40%	Discontinue study
5 80 mg daily	Y	≥ 40%	Increase dose to prava 120 mg and enroll additional participants
6 120 mg daily	N	=	Discontinue study
7 120 mg daily	Y	<40%	Discontinue study
8 120 mg daily	Y	≥ 40%	Increase dose to prava 160 mg and enroll additional participants
9 160 mg daily	N	=	Discontinue study
10 160 mg daily	Y	=	Study complete

Safety/tolerability: Y= Yes; <3 participants with  $\geq$  one grade 3 (or higher) event of musculoskeletal symptoms, creatine kinase elevation, or liver function test elevation attributed to study drug (probable or definite)

N= No; For Arm 1 (pravastatin 40 mg daily):  $\geq$  1 participant with  $\geq$  one grade 3 (or higher) event of musculoskeletal symptoms, creatine kinase elevation, or liver function test elevation attributed to study statin medication (probable or definite).

For Arms 2, 3, and 4:  $\geq$  3 participants with  $\geq$  one grade 3 (or higher) event of musculoskeletal symptoms, creatine kinase elevation, or liver function test elevation attributed to study statin medication (probable or definite)

$AUC_{0-24}$ = Area-under-the-plasma-concentration-time curve for 24-hour exposure

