#### ***Decision-making algorithm for initiating new dosing cohorts***

The study will be monitored by a DSMB, which will review the safety data for each cohort and will give approval before initiation of each possible dose escalation. Specifically, study drug dose will not be escalated and the study if any three participants develop grade 3 or higher musculoskeletal/CK-related adverse events (AEs), LFT-related AEs ( $> 5 \times UNL$  without symptoms, but  $> 3 \times UNL$  with symptoms or bilirubin  $> 2 \times ULN$ ) or any type of grade 4 event regardless of causal attribution. Study drug dosage will be escalated only if the dose is deemed safe/tolerable based on the above rules and the mean pravastatin AUC is reduced by  $\geq 40\%$  relative to the pre-Rifafour value. Study participants in whom the study drug has been discontinued will remain in the study until the final clinical visit and laboratory evaluation. In the event of study product discontinuation, management of the standard-of-care TB drugs will revert to the site clinician as per national guidelines.

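### The on-treatment drug rules do not carry forward the entry bar on erythromycin, leaving a minor, avoidable muscle-safety risk while pravastatin is given on Days 1–15

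*Combined protocol and SAP*

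**What the plan says.** **At entry.** Section 11, exclusion criterion q, rules out "Planned or current use of cyclosporine, tacrolimus, erythromycin or colchicine". Criterion b rules out current statins and other lipid-lowering agents, and criterion e rules out antiretrovirals.

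**Why erythromycin matters.** Section 13, Pravastatin, Drug-drug interactions: "Medications that may cause drug interactions with pravastatin include fibrates, erythromycin, niacin, and many others". The stated possible result is "increased levels of medicine in the blood and an increased risk of developing serious muscle problems".

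**On treatment.** Section 4, Concomitant medications, prohibits a named list of antimicrobials with antituberculous activity and a second statin. Erythromycin is not on the list. The section then says: "Antimicrobials with no known antituberculous activity may be prescribed for intercurrent infections at the discretion of the investigator".

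**A contrasting case.** Section 12, HIV-Infected Individuals, carries the antiretroviral bar past enrolment: "If a participant is already enrolled in the study, and they require antiretroviral therapy, they will be taken off of study medicines".

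**Detection of muscle effects.** The checklist in Section 4, Targeted symptom assessment, ends "numbness/tingling of extremities, headache, joint pain, eye pain". It names joint pain but not muscle pain, which is left to an open question about other symptoms. CK is scheduled at screening and on Days 7, 15, 21 and 30, and it is not on the unscheduled-visit list. Section 5 requires CK when myalgia reaches Grade 3.

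**The concern.** The protocol treats erythromycin as unsuitable alongside pravastatin at entry and says why. The word planned in criterion q catches a course foreseen at screening. It does not catch a new infection arising on Days 1–15, which is the situation that the discretion sentence covers. There the stated rule permits what the entry rule refuses.

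Two things are at stake. One is participant safety: an avoidable exposure that the protocol itself links to muscle harm, in a study that may reach 160 mg, twice the highest recommended dose. The other is interpretation: a CK or muscle event in someone taking both drugs is harder to attribute to the pravastatin dose, and muscle and CK events are among those that the escalation decisions count.

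**Working it through.** **1. Which entry bars continue on treatment**

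| Drug | Barred at entry | Position on treatment |
|---|---|---|
| Statins | Criterion b | A second statin is prohibited (Section 4) |
| Antiretrovirals | Criterion e | Participant stops study medicines (Section 12) |
| Erythromycin | Criterion q | Not prohibited; falls to investigator discretion |
| Colchicine | Criterion q | Not addressed |
| Other lipid-lowering agents | Criterion b | Not addressed in Section 4 |
| Cyclosporine, tacrolimus | Criterion q | Not in Section 4; listed as contraindicated with rifampin (Section 13, Rifampin) |

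The discontinuation criteria in Section 9 do not mention interacting drugs. Section 5, Other toxicities, allows concomitant drugs to be held once toxicity is suspected, which is not a bar. The documents do not expressly class erythromycin as lacking antituberculous activity; that is inferred from its absence from the list. On either reading it is not named as prohibited.

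**2. Illustrative size of the CK risk**

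Section 13, Tolerability, reports CK above 10 × ULN in 4 of 464 patients at 80 mg over a mean of 8.6 months, and in 0 of 115 at 40 mg. These are background rates; they do not measure the interaction. A constant rate is assumed.

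- Follow-up: 8.6 × 30.44 = 262 days.
- 80 mg: h = −ln(1 − 4/464)/262. Over 15 days, 1 − exp(−15h) = 0.0005, or 0.05%.
- 40 mg: one-sided 95% upper bound 1 − 0.05^(1/115) = 2.6%, or about 0.15% over 15 days.
- Assumed 10- to 50-fold increase on the 80 mg rate: 0.49% to 2.45% per exposed participant.
- Assumed use q of 1% to 10%: chance of at least one exposed participant in an arm of 10 is 1 − (1 − q)^10 = 9.6% to 65%.
- Chance of an interaction event in that arm, about 10 × q × risk: 10 × 0.01 × 0.0049 = 0.05% up to 10 × 0.10 × 0.0245 = 2.5%.
- Arm 1 (n = 5), taking the 80 mg rate: 5 × 0.01 × 0.0049 = 0.025% up to 5 × 0.10 × 0.0245 = 1.2%. The 40 mg upper bound is three times the 80 mg rate (0.15/0.05) and would roughly triple these.

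**3. Set against the decision rules**

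- The safety/PK decision table fails Arms 2–4 on three participants and Arm 1 on one, in each case with probable or definite attribution to the statin.
- The rule for new dosing cohorts also needs three, and states no attribution requirement for grade 3 CK events.
- Three interaction events in an arm of 10, at the extreme assumptions: 120 × (0.10 × 0.0245)³ = 120 × 0.00245³ ≈ 2 in a million.
- The Data Analysis section fails any arm on one discontinuation judged pravastatin-related. There the one-event figures in step 2 apply. That this rule differs from the other two is a separate matter.

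**4. The 40% AUC rule (80 mg and 120 mg arms)**

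Assume a geometric mean over 10 participants; the plan says only mean. If k participants have their Day 15 AUC raised f-fold, the largest true reduction that would be pushed below 40% is 1 − 0.60/f^(k/10).

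| | f = 1.25 (assumed) | f = 2 (assumed) |
|---|---|---|
| k = 1 | 41.3% | 44.0% |
| k = 3 | 43.9% | 51.3% |

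With the plan's within-subject CV of 33%, SE = √ln(1 + 0.33²) × √(2/10) = 0.144 on the log scale. Multiplied by t = 1.833 on 9 degrees of freedom, this gives 0.264, in line with the plan's stated 26% half-width. The shift from one exposed participant, ln(f)/10 = 0.022 to 0.069, is less than half of one SE.

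**The case against.** The strongest reply is that discretion is itself a control before exposure. The prescriber works under a protocol that contains both criterion q and the interaction warning. Participants are assessed daily, are asked to contact the site before going elsewhere, and can be taken off study treatment under Section 9 whenever the investigator judges it in their interest. So a reader who infers that every safeguard acts only after exposure would be wrong. What remains is that none of these is a prohibition, and the one sentence that addresses new infections points the other way.

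The pharmacology also tempers the risk. Section 13 says that pravastatin is not significantly metabolised by CYP enzymes and is less prone to interactions than other statins, and that rifampin lowers its exposure by 30–50%. The warning covers a group of drugs that may interact and gives no figure specific to erythromycin. The antiretroviral precedent is accompanied by a quantified effect (efavirenz lowers pravastatin AUC by about 40%); nothing comparable is given here. All of this stands and keeps the point minor.

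A reader might further infer that the gap could decide whether an arm passes or whether the dose is escalated. The documents do not support that. Every figure for an interaction effect rests on assumed inputs. Arms 2–4 need three participants under both escalation rules. Arm 1 needs only one, but with probable or definite attribution, which a recorded confounder makes less likely. One exposed participant moves the AUC estimate across 40% only when the reduction is already close to 40%.

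**Conclusion.** The gap in the text is certain: erythromycin is barred at entry for a stated reason and is not barred while pravastatin is given. The consequence is a minor, avoidable safety risk whose size cannot be derived from the documents, plus possible difficulty in attributing a CK or muscle event. Under deliberately wide assumptions (1–10% use, 10- to 50-fold increase on the 80 mg background rate), the chance of one interaction CK event in an arm of 10 is about 0.05% to 2.5%. No material effect on the arm decisions or the 40% AUC rule is shown. The case for change rests on a named risk that costs almost nothing to remove, and not on these figures.

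**What to change.** In Section 4, Concomitant medications:

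- Add erythromycin to the drugs not to be used during study phase therapy. For consistency, add colchicine, other lipid-lowering agents, and cyclosporine and tacrolimus (the last two are already listed as contraindicated with rifampin).
- Make the sentence on antimicrobial discretion subject to that list.
- If such a drug is clinically unavoidable, the investigator decides under Section 9 whether pravastatin stops. The participant stays in the safety data, and the exposure is reported to the DSMB.
- Exclude the Day 15 AUC from the 40% rule, and replace the participant for PK, only if the drug was taken close enough to Day 15 to affect that profile. Set the window in advance, so that a short early course does not discard a valid profile. Say that this window decides PK evaluability, because the section's existing classification after more than two doses of a listed drug would otherwise leave it unclear.

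The cost is a few lines and an occasional PK replacement. At the assumed 1–10% use, 30 × 0.01 = 0.3 to 30 × 0.10 = 3 of the 30 participants in Arms 2–4 would be exposed at all, and the window would spare some of them. The plan already allows for this: Section 9 replaces participants who stop early, and the Data Analysis section recruits those arms until 10 are evaluable. Necessary treatment is not withheld.

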### ***Administration of study drug***

Patients should start on assigned study drug (pravastatin) as soon as possible after recruitment. Doses of study drug will be given as directly observed therapy (DOT) by study personnel, or by a health care worker or lay treatment supervisor who is aware of the study protocol and trained regarding the study protocol. Alternatively, doses of study drug can be given via DOT by a family member or employer who has been trained by the study team. Adherence will be confirmed by review of the participant's treatment card, and retraining of the DOT provider will be provided if needed. Adherence will be defined as the number of prescribed doses taken. DOT may be administered at the TB clinic or other health care facility, or, with the participant's permission, at the participant's residence, workplace, or other mutually agreed upon location convenient for the participant.

HRZE will not be provided by the study team.

### ***Obtaining sputum specimens***

Sputa should be obtained by spontaneous expectoration whenever feasible. Sputa should be refrigerated at approximately 4 degrees Celsius after collection, and transported to the laboratory as soon as possible but within 2 working days of collection (i.e. received in the laboratory within 2 working days of collection).

### ***Laboratory aspects of sputum analysis***

Laboratory evaluation of sputa will be performed at a qualified mycobacteriology reference laboratory and will be done according to detailed written lab SOPs. Briefly, sputa will be homogenized and decontaminated using the NALC-NaOH method. Fluorescence smear microscopy will be performed on an aliquot of the concentrated processed specimen. Aliquots will be added to Lowenstein Jensen (solid) media and MGIT (liquid) media. Nucleic acid and/or biochemical methods will be used for mycobacterial species determination. Quality monitoring procedures will be documented, and laboratory activities will be participant to regular study monitoring. Sputum collection will not occur after Friday of each week, as the protocol requires transport of specimens to the laboratory within 2 working days of sputum collection.

### ***Steady State Pharmacokinetic Assessments***

*Intensive PK sampling:* Each participant will have initial PK assessments for pravastatin at Day 1 (immediately prior to dose administration and at 0.5, 1, 1.5, 2, 3, 4, 6, and 8 hours post-dose) as well as single point PK assessment on Day 2 (trough level immediately before the 2nd dose and 4-6 hours after the 2nd dose of pravastatin). The post-dose PK assessment on Day 2 will be completed prior to the administration of the first dose of TB medications. Each participant will also have steady-state PK assessment at Day 15 immediately prior to administration of study medications and then at 0.5, 1, 1.5, 2, 3, 4, 6, and 8 hours post-dose. Samples will consist of 4cc of blood collected via an indwelling catheter or by direct venipuncture.

For participants who miss or vomit the first dose of pravastatin on Day 1, that visit should be rescheduled  $\geq 1$  day later and study procedures recommenced. For participants who miss or vomit pravastatin dose on Day 2, that visit should be rescheduled within 2 days if possible, holding the first dose of TB medications until after these Day 2 PK draws. For participants who miss doses on one of the two days preceding the PK collection on Day 15 (steady state) or who vomit that day's doses, the Day 15 visit should be rescheduled for  $\geq 2$  days later.

Specimens will be obtained, processed, and assayed according to the PK standard operating procedures manual.

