The Screening evaluation process itself may occur over a few days with more than one visit, however, all Screening evaluations will be obtained within 3 days of study entry.

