***Sample size***

The sample size will be between 5 and 35 evaluable participants, who will be recruited into the following arms: 1) Standard-of-care regimen (Rifafour) + pravastatin 40 mg daily (5 evaluable participants); 2) Standard-of-care regimen (Rifafour) + pravastatin 80 mg daily (10 evaluable participants); 3) Standard-of-care regimen (Rifafour) + pravastatin 120 mg daily (10 evaluable participants); 3) Standard-of-care regimen (Rifafour) + pravastatin 160 mg daily (10 evaluable participants). Participants in Arms 2, 3, and 4 (10 participants each) will only be recruited if necessary, i.e., if pravastatin 40 mg is well tolerated and safe, and if escalated doses are also tolerated and safe, yet drug exposures are reduced by  $\geq 40\%$  in participants due to the known interaction with rifampin.

A sample size of 10 evaluable participants for pravastatin PK analysis was chosen based on within-subject variability (CV%) of statin AUC in interaction studies ranging from 6-60% and a within-subject coefficient of variation (CVw) of 33%. With 10 evaluable participants per arm, the precision (i.e., half width of the 90% confidence interval on the log scale) for the treatment difference will be within 26% of the point estimate for AUC. If the point estimate of the ratio of geometric mean is 1, then 90% confidence interval will be approximately (0.74, 1.35).

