## ***Data Analysis***

The current study is a 2-week, 4-arm dose-escalation trial to determine the safety/tolerability and PK of pravastatin when co-administered with the standard drug regimen for drug-susceptible TB (Rifafour). Participants will receive standard anti-TB therapy and pravastatin beginning at a dose of 40 mg once daily. Each subsequent arm (pravastatin 80 mg, 120 mg, and 160 mg) of this study will continue to recruit participants until at least 10 participants in each group are evaluable for full PK analysis.

The primary endpoints in this study are safety/tolerability and pravastatin exposures. A regimen will be deemed safe and well tolerated if none of the participants require treatment discontinuation for a pravastatin-related adverse reaction and  $\leq 3$  participants experience a pravastatin-related grade 3 (or higher) adverse event during the 14-day study period and follow up. PK parameters (e.g., area under the concentration-time curve over 24 hours ( $AUC_{0-24}$ ), minimum concentration ( $C_{min}$ ), maximum concentration ( $C_{max}$ ), and oral clearance (Cl/F)), will be estimated for pravastatin from intensive sampling data after a single dose of pravastatin (baseline PK, prior to initiation of TB treatment) and after 14 days of co-administration with the first-line anti-TB regimen. Based on PK data of pravastatin when co-administered with rifampin ( $T_{max} = 1$  hour,  $T_{1/2} = 1.5$  hours), plasma samples will be collected for pravastatin measurements by LC-MS/MS at the following time points: pre-dose, 0.5 hrs, 1 hr, 1.5 hrs, 2 hrs, 3 hrs, 4 hrs, 6 hrs, and 8 hrs. Pravastatin exposures will be calculated using a noncompartmental approach using standard PK software, e.g., Phoenix WinNonLin. Using all PK data, a PK/PD model will be developed to evaluate the relationship between drug exposures (e.g.,  $C_{max}$ ,  $T_{max}$  or  $AUC_{0-24}$ ) and outcomes (e.g., safety/tolerability).  $C_{max}$  and  $t_{max}$  will be taken directly from the original data. The terminal log-linear phase of the plasma concentration-time curve will be identified visually for each curve.

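### After a vomited Day 2 pravastatin dose, the first TB dose is held for a targeted 1 to 2 days to repeat one sample that neither the AUC comparison nor the escalation rule uses

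*Combined protocol and SAP*

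**What the plan says.** Section 4 (Steady State Pharmacokinetic Assessments) plans nine pravastatin samples on Day 1, two on Day 2 and nine on Day 15. The Day 2 pair is a trough just before the second dose and one sample 4 to 6 hours after it. Appendix 1, footnote 8, labels this sparse sampling, although the Day 2 visit list calls it intensive. On the order of events: "The post-dose PK assessment on Day 2 will be completed prior to the administration of the first dose of TB medications". If the Day 2 dose is missed or vomited, "that visit should be rescheduled within 2 days if possible, holding the first dose of TB medications until after these Day 2 PK draws". No maximum hold is set, and there is no instruction for a visit that cannot be rearranged in that time. I found no reason given for the hold; section 7, on departures from routine care, is marked not applicable.

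In section 18 (Data Analysis), the baseline PK parameters are those estimated "after a single dose of pravastatin (baseline PK, prior to initiation of TB treatment", and they are compared with those after 14 days of co-administration. The listed sampling times run from pre-dose to 8 hours. Separately, "Using all PK data, a PK/PD model will be developed", to relate exposure to outcomes such as safety. Each arm from 80 mg upward recruits "until at least 10 participants in each group are evaluable for full PK analysis".

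Section 9 stops study treatment in a participant who misses more than two doses or fails to complete a PK sampling visit.

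**The concern.** Participants have pulmonary TB confirmed by Xpert with a cycle threshold below 28. Exclusion criterion k removes anyone "Currently receiving TB treatment". Up to five days of treatment in the previous three months is allowed, but a participant whose first TB dose is held receives no TB drugs during the hold.

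Delaying treatment for a research sample needs a reason in the analysis. Repeating a vomited Day 1 dose has one, because Day 1 supplies the baseline AUC on which escalation depends. The Day 2 rule does not obviously have a comparable purpose. At stake is a short, avoidable delay in a few participants, set against one sparse sample.

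**Working it through.** No figure in the plan is in dispute, so the check follows the Day 2 samples through the analysis.

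**1. What a vomited dose spoils.** The trough is drawn before the second dose and is unaffected. Only the sample at 4 to 6 hours is lost. A pre-dose draw repeated at a visit 1 to 2 days later would fall 24 + 24 = 48 to 24 + 48 = 72 hours after the Day 1 dose, so it could not replace the 24-hour trough.

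**2. Where that sample could be used.**

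| Planned use | Data it rests on | Uses the Day 2 post-dose sample? |
|---|---|---|
| Baseline AUC, Cmax, half-life (Data Analysis) | Profile after the single Day 1 dose; the Day 2 trough could serve as its 24-hour point | No |
| Co-administration AUC (Data Analysis) | Day 15 profile | No |
| Paired comparison (Data Analysis) | Those two profiles | No |
| Escalation (both decision algorithms) | Safety, and a mean AUC reduction of at least 40% from the pre-Rifafour value | No; one sample after a second dose gives no AUC |
| PK/PD model (Data Analysis) | All PK data | Possibly |

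**3. What is lost if it is not repeated.** Off-rifampin samples per participant: 9 + 2 = 11. All samples: 11 + 9 = 20. An affected participant loses 1 of 11 off-rifampin samples (1 of 20 overall), 0 of 9 Day 1 points and 0 of 9 Day 15 points.

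**4. Length of the hold.** The planned first TB dose is on Day 2 (Appendix 1, footnote 6). A visit rescheduled within 2 days moves it to Day 3 or Day 4, a delay of 1 to 2 days if the target is met. Some of this may be needed anyway before the patient can keep oral drugs down. If TB drugs instead start the same day or the next day, the delay is 0 to 1 day. The saving is therefore between 1 - 1 = 0 and 2 - 0 = 2 days.

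**5. Missed visit.** Dosing is directly observed, so I take a missed Day 2 dose to mean, as a rule, a missed visit. The absence itself then causes the delay. At the next attended visit the rule adds only the 4 to 6 hours that every participant waits.

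**6. Knock-on rules.** Section 9 does not say whether a missing Day 2 post-dose sample counts as an uncompleted PK visit. Data Analysis does not say whether it makes a participant non-evaluable. Changing section 4 alone would leave both questions open.

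**The case against.** The strongest defence is that off-rifampin data cannot be collected once Rifafour starts, and that the model is planned on all PK data. Keeping an observation that cannot be repeated is an ordinary trade-off, not an error. That stands, and it is why this is an improvement to consider rather than a fault in the analysis.

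A second point is attribution. Safety and tolerability are primary, section 5 assesses each adverse event against both pravastatin and Rifafour, and section 13 lists nausea and vomiting for rifampin and isoniazid. Starting four drugs soon after a vomited pravastatin dose could make further vomiting harder to attribute. The protocol does not give this as its reason, but it is a fair, small cost.

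Third, there are safeguards. Eligibility excludes CNS TB, HIV infection with CD4 below 350, haemoglobin below 8 g/dL and a Karnofsky score below 60. Section 9 allows withdrawal for safety, stops treatment after more than two missed doses, and requires calls and a home visit after a missed visit. These soften the hold; none caps or removes it, and withdrawal ends study treatment.

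A reader might infer more than the documents support:
- *That the hold is open-ended.* The target is 2 days, the wording leaves the site discretion, and the section 9 rules apply. What is missing is a firm cap.
- *That the rule causes a delay of 5 to 6 days.* The protocol says "all Screening evaluations will be obtained within 3 days of study entry". If entry is Day 1, screening to first TB dose is already up to 3 + 1 = 4 days; the hold adds 1 to 2. Most of the total is routine.
- *That missed visits raise the same problem.* There the rule adds hours, not days.
- *That the sample has no value and should be dropped for everyone.* It is the only one after a second off-rifampin dose, and the model may use it. Dropping it throughout is a preference.

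**Conclusion.** The point holds for a vomited Day 2 dose only. The protocol then holds TB treatment for a targeted 1 to 2 days, without a firm cap, to repeat one sample that neither the AUC comparison nor the escalation rule uses.

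The effect is small. The documents give no frequency for vomited Day 2 doses, so none or a few of at most 35 participants may be affected. They also give no figure for harm from a delay of this length, and part of the delay may be clinical. No planned comparison is biased. The conclusion assumes that the trough was drawn on schedule and that the baseline AUC comes from the Day 1 dose, as Data Analysis states. It is a cheap improvement in participant care.

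**What to change.** - **Section 4, Steady State Pharmacokinetic Assessments.** After a vomited Day 2 pravastatin dose, TB medications start the same day once oral drugs are tolerated, or the next day at the latest. If the post-dose sample cannot be taken before then, it is recorded as missing.
- **Same section, missed Day 2 visit.** Keep the current order at the next attended visit: trough, pravastatin, sample at 4 to 6 hours, then TB drugs the same day.
- **Section 9.** A missing Day 2 post-dose sample does not count as an uncompleted PK sampling visit and does not trigger discontinuation.
- **Section 18, Data Analysis.** A participant who lacks only that sample remains evaluable for the full PK analysis.

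The cost is a short amendment to three sections. In affected participants the exploratory model loses its one sample after a second off-rifampin dose, and attributing further vomiting to pravastatin or Rifafour may be slightly harder. The AUC comparison and the escalation rule lose nothing.
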